4.1.12.1 Monotone Data Pattern

Prior to imputation, intermittent missing HbA1c/FPG values (i.e., missing values both preceded and followed by at least one non-missing value) will be imputed under a “missing at random” (MAR) model for missing data using a Markov chain Monte Carlo (MCMC) method of imputation.

Since in general the missing pattern will not be monotone, the first step for any of the methods presented below will be to use the Markov Chain Monte Carlo (MCMC) method in conjunction

with the MONOTONE statement of the SAS MI procedure to partially impute quantitative parameters, separately for each treatment regimen (i.e. low-dose, low-dose/high-dose and placebo) and by weight, to create imputed datasets with just enough missing quantitative values to generate two hundred (200) imputed data sets with a monotone missing data pattern (for each treatment regimen), assuming a MAR missing data pattern. Subjects withdrawing from IP before the up-titration will be assigned a weight of 1 and will be included in each imputation model (low-dose and low-dose/high-dose regimen). Indicators of randomisation strata (as described in Section 4.1.12) and visit (i.e., baseline HbA1c/FPG along with all visits per protocol up to Week t) will be the parameters included in MCMC models.

The random seed number for the MCMC stage will be 2717.

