1.2 Study design

The proposed study is a 26-week Phase 3b, multicentre, randomised, placebo-controlled, double-blind, parallel-group study with a 26-week safety extension period to evaluate the safety and efficacy of dapagliflozin (5 mg and 10 mg), and, separately, saxagliptin (2.5 mg and 5 mg) in paediatric subjects with T2DM, and an additional post-study visit at Week 104 for assessment of measures of growth and maturity.

This study will consist of 4 study periods:

- (i) **Screening period.** This period starts with enrolment and ends at the start of the lead-in period.
- (ii) **Lead-in period.** During this 2-week period, subjects will be instructed on a diet and exercise program (in accordance with the American Diabetes Association [ADA] or similar local guidelines) to be followed for the study duration. Subjects will maintain their baseline types and/or doses of antidiabetic therapy throughout the study. No placebo or study medication will be provided during the lead-in period.
- (iii) **26-week double-blind short-term (ST) treatment period.** On the Day 1 visit, subjects who meet all protocol-specific enrolment and randomisation criteria will be randomised.
- (iv) **26-week double-blind long-term (LT) treatment period.** After completing the ST treatment period, all subjects will enter the 26-week LT treatment period.

The 52-week treatment period will be referenced as the ST+LT treatment period.

The **Randomised withdrawal period** is defined, for those subjects eligible for the 3rd randomisation, as the time from 3rd randomisation (Week 32 or Week 40) until end of LT period (Week 52).

Subjects who discontinue IP treatment before the end of the study treatment period will enter a non-treatment, follow-up phase in which subjects will follow their visit schedules with modified assessments until study completion.

In addition, there will be 2 post-study visits:

- (i) **Week 56** (phone visit), to assess AEs and serious adverse events (SAEs).
- (ii) **Week 104** (office visit), to assess measures of growth and maturity, height, weight, AEs and SAEs.

Approximately 243 paediatric subjects aged 10 to below 18 years of age will be randomised in a 1:1:1 ratio to receive dapagliflozin 5 mg, saxagliptin 2.5 mg, or placebo. Approximately 81 subjects will be randomised to each treatment arm.

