1.3 Number of subjects

The sample size for this study was selected to be consistent with the research hypotheses.

Dapagliflozin and saxagliptin will be compared with placebo separately. Within each group of hypotheses, multiplicity adjustment with respect to the comparisons will be made using a hierarchical approach. No comparisons between dapagliflozin and saxagliptin will be performed.

The sample size for this study is based on the ability to detect a 0.75% improvement over placebo for dapagliflozin or saxagliptin in change from baseline in HbA1c at Week 26 (ST) with approximately 80% power for each comparison at a two-sided alpha level of 0.05. If 243 paediatric subjects are randomised and analysed, and each treatment compared to placebo at a 2 sided alpha=0.05 level, this will provide approximately 80% power for each comparison to detect a 0.75% reduction in HbA1c change from baseline versus placebo assuming a standard deviation of 1.7%.

Day 1 Randomisation will be stratified based on the baseline anti-diabetic treatment regimen (stable baseline dose of metformin [IR or XR], a stable baseline dose of insulin, or a stable combination of metformin [IR or XR] and insulin), sex, and age (≥ 10 to < 15 years, ≥ 15 to < 18 years).

The standard deviation estimate of 1.7% is based on a blinded review of the ongoing study data.

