\mathbf{W}_1 : For the comparison of the low-dose/high-dose treatment regimen versus placebo (used for secondary endpoints), all dapagliflozin and saxagliptin subjects who had HbA1c < 7% at Week 12 and remained on the low-dose will be assigned a weight of 1. The dapagliflozin and saxagliptin subjects who had HbA1c \geq 7% at Week 12 and continued on the low-dose will be assigned a weight of 0. The dapagliflozin and saxagliptin subjects who had HbA1c \geq 7% at Week 12 and received the high-dose will be assigned a weight of 2. All subjects who do not undergo the second randomisation and all placebo subjects will be assigned a weight of 1.

\mathbf{W}_2 : For the comparison of the low-dose treatment regimen versus placebo (used for secondary endpoints), all dapagliflozin and saxagliptin subjects who had HbA1c < 7% at Week 12 and remained on the low-dose will be assigned a weight of 1. The dapagliflozin and saxagliptin subjects who had HbA1c \geq 7% at Week 12 and continued on the low-dose will be assigned a weight of 2. The dapagliflozin and saxagliptin subjects who had HbA1c \geq 7% at Week 12 and received the high-dose will be assigned a weight of 0. All subjects who do not undergo the second randomisation and all placebo subjects will be assigned a weight of 1.

For the comparison of overall drug treatment versus placebo (used for the primary endpoint analysis and some secondary endpoints) no weighting will be used (i.e. all treatment groups will be assigned a weight of 1).

It follows that parameters can be estimated with appropriate design and weight matrix by

$$\hat{\beta} = (X'WX)^{-1}X'WY \sim N(\beta, \Sigma)$$

such that $\hat{\beta} = [\hat{\beta}_{Intcpt} \quad \hat{\beta}_{Tr} \quad \hat{\beta}_{Base} \quad \hat{\beta}_{Strata}]^T$

and the design matrix for i -th subject $x_i = [1 \quad Trt \quad x_{baseline} \quad Y_{Strata}]$.

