4.1.12.5 Multiple imputation under MAR hypothesis

Using the monotone datasets generated as described in Section 4.1.12.1, the remaining missing HbA1c or FPG data will be imputed separately for each treatment regimen and weight (as applicable) using a REGRESSION method in conjunction with the MONOTONE statement of the SAS MI procedure and MAR assumption.

- Step 1: Prior to imputation, the MCMC method will be used in the MI procedure to impute just enough missing values under a “missing at random” (MAR) model to generate 200 imputed data sets with a monotone missing data pattern. The imputation model will include factors and covariates in the following order: indicators of randomisation strata and baseline HbA1c/FPG as well as HbA1c/FPG at all visits per protocol prior to Week t.
- Step 2: Missing data will be imputed sequentially at each assessment using a MAR imputation based on all non-missing data from that visit and data from all prior visits (after imputation). The indicators representing randomisation strata will be included in the same order as described in Step 1. Therefore, the model will include, in the following order, indicators representing randomisation strata of sex, age group, and background medication as well as, baseline HbA1c/FPG, treatment regimen, and all previous HbA1c/FPG values (all visits per protocol prior to Week t).
- Step 3: Imputed values from each of the 200 imputation datasets selected from Step 2 and the non-missing data will be analysed by ANCOVA applied at Week t, with terms for baseline HbA1c, randomisation strata, and treatment regimen as described in Section 4.1.9. In case of non-convergence, the imputation model will be simplified removing/collapsing the randomisation strata indicator variables in a stepwise manner as described in Section 4.1.
- Step 4: Results from each ANCOVA model will be combined as described in Section 4.1.12.4.

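### By-weight MAR imputation in the regimen sensitivity analyses draws early active-arm drop-outs' Week 26 values from a model fitted almost entirely to Week 12 responders, which favours the drug

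*SAP*

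**What the plan says.** SAP 4.1.9 sets the weights for the regimen comparisons. In W1 (low-dose/high-dose) and W2 (low-dose), active-arm subjects "who had HbA1c < 7% at Week 12 and remained on the low-dose will be assigned a weight of 1". Week 12 non-responders get 0 or 2, depending on the dose they were re-randomised to and the regimen being tested. The section adds: "All subjects who do not undergo the second randomisation and all placebo subjects will be assigned a weight of 1".

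SAP 4.1.12.1 carries this into the imputation: "Subjects withdrawing from IP before the up-titration will be assigned a weight of 1", and these subjects enter the models for both regimens. The preliminary MCMC step is run "separately for each treatment regimen (i.e. low-dose, low-dose/high-dose and placebo) and by weight".

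SAP 4.1.12.5 governs MAR imputation. Missing HbA1c or FPG values "will be imputed separately for each treatment regimen and weight (as applicable) using a REGRESSION method".

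SAP 4.5.2.1 and 4.5.3.1 (HbA1c) and 4.5.5.1 and 4.5.6.1 (FPG) repeat the two regimen-versus-placebo comparisons. They drop data after rescue or treatment discontinuation and impute by 4.1.12.5.

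SAP 4.4.2.1, the corresponding sensitivity analysis for the primary endpoint, describes the donors differently: other subjects on the same regimen who finished short-term treatment without rescue. It makes no mention of weight class.

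**The concern.** Regression imputation under MAR needs donors who are comparable with the drop-outs given the observed predictors. In the active arms, weight 1 pools two kinds of subject: those who stopped before the second randomisation, and those retained at low dose because their Week 12 HbA1c was below 7%. Once off-treatment data are removed, the first kind has no Week 26 value, so the model is fitted almost entirely to the second. For a drop-out with no Week 12 value, that is selection on the outcome, and it distorts the result even if drop-out is completely random.

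All placebo subjects have weight 1, so placebo drop-outs are imputed from the whole placebo arm. The error is therefore one-sided. At stake are the sensitivity analyses for tests 1, 2, 4 and 5 in the SAP 4.5.1 hierarchy. A robustness check should not lean towards the drug by construction.

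**Working it through.** **The plan's own figure.** SAP 1.3 states "approximately 80% power for each comparison to detect a 0.75% reduction in HbA1c change from baseline versus placebo assuming a standard deviation of 1.7", "with approximately 80% power for each comparison at a two-sided alpha level of 0.05", and SAP 1.2 states "Approximately 81 subjects will be randomised to each treatment arm".
- Standard error of a difference: 1.7 × √(2/81) = 0.267.
- Power: Φ(0.75/0.267 − 1.96) = Φ(0.85) = 0.80 (0.802 by the normal formula, 0.797 by noncentral t).

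The stated power reproduces, and this point does not alter it.

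**Who supplies Week 26 data in the active arms once off-treatment data are dropped**

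| Subjects | Weight | Week 26 value available |
|---|---|---|
| Week 12 responders still on treatment, not rescued | 1 | yes |
| Stopped before second randomisation | 1 | no |
| On treatment but not re-randomised for another reason | 1 | possibly; expected to be few |
| Re-randomised non-responders in the regimen tested | 2 | yes, if on treatment and not rescued |
| Re-randomised non-responders in the other regimen | 0 | not used |

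**Share of the regimen mean.** Let r be the proportion of responders and d the proportion of early drop-outs. The rest, 1 − r − d, are split 1:1 into weights 2 and 0. Total weight per subject is r + d + 2 × (1 − r − d)/2 = 1, so early drop-outs carry share d. The shift in the regimen mean is d × (bias per early drop-out).

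**Bias per early drop-out, by simulation.**
- From the documents: SD of change 1.7, baseline range 6.5-10.5%, visits at Weeks 6, 12, 20 and 26, cut-off of 7% at Week 12.
- Assumed, not in the documents: baseline mean 8.0 and SD 1.1 before truncation; mean Week 26 change of 0, -0.25 or -0.75; correlation between successive visits of 0.70 or 0.85; SD growing with √(time); drop-out independent of outcome; everyone followed on one regimen.

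Sequential regression was fitted to Week 12 responders only, and then to all remaining subjects. Bias is imputed minus true mean Week 26 HbA1c, in percentage points, with responders as donors:

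| Mean change | Correlation | Responders | Baseline only | Observed to Week 6 | Observed to Week 12 |
|---|---|---|---|---|---|
| -0.75 | 0.70 | 38% | -0.92 | -0.68 | -0.02 |
| -0.75 | 0.85 | 38% | -1.36 | -0.66 | 0.00 |
| -0.25 | 0.70 | 27% | -1.13 | -0.86 | +0.02 |
| -0.25 | 0.85 | 27% | -1.68 | -0.87 | +0.03 |
| 0 | 0.70 | 22% | -1.27 | -0.98 | -0.01 |
| 0 | 0.85 | 22% | -1.88 | -1.06 | +0.02 |

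With all remaining subjects as donors, bias lay between -0.01 and +0.02 throughout.

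**Shift in the active-regimen mean, no Week 12 value**
- d = 5% (about 4 of 81): 0.05 × 0.66 = 0.03 to 0.05 × 1.88 = 0.09, downwards.
- d = 10% (about 8 of 81): 0.10 × 0.66 = 0.07 to 0.10 × 1.88 = 0.19, downwards.

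Against the planned effect this is 0.03/0.75 = 4% to 0.19/0.75 = 25%. Against the unadjusted standard error it is 0.03/0.267 = 0.1 to 0.19/0.267 = 0.7.

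**The case against.** The strongest reply is that the SAP may not intend this. The by-weight rule in 4.1.12.5 applies only where applicable, and 4.4.2.1 names completers of the same regimen as donors, which is close to the remedy proposed here. This stands as evidence of inconsistency, but it does not remove the problem. Where the SAP wants no weights in the imputation it usually says so (for example 4.4.1, 4.5.4 and 4.5.10). Sections 4.5.2.1, 4.5.3.1, 4.5.5.1 and 4.5.6.1 carry no such sentence. The parent sections prescribe W1 or W2 while pointing back to 4.4.1, which is unweighted. A programmer following 4.1.12.5 literally obtains the biased version.

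Second, the plan tries to collect the data that would limit the bias. HbA1c is scheduled at early treatment discontinuation (Protocol Table 5.1-2). SAP Table 8 keeps values up to 8 days after last dose, and Table 9 assigns days 65-113 to Week 12. This stands in part: drop-outs with a Week 12 value show almost no bias. But a subject whose last dose falls before day 57 (65 − 8) cannot have a Week 12 value in this analysis.

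Third, whole-arm donors are not a complete cure. In a separate simulation (baseline about 8.1%, SD of change 1.65, about 40% responders, 5-10% early drop-out) where poorer responders dropped out more often, bias in the regimen mean was -0.04 to -0.18 by weight and -0.01 to -0.05 with whole-arm donors. Some bias remains, but less.

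Finally, only HbA1c was simulated. The selection is on Week 12 HbA1c, so any effect on FPG depends on a correlation the documents do not give.

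**Conclusion.** The concern holds for the weighted MAR sensitivity analyses of the regimen comparisons. If 4.1.12.5 is applied by weight, active-arm early drop-outs without a Week 12 value are imputed too low, and placebo drop-outs are not. For HbA1c the active-regimen mean moves by roughly -0.03 to -0.19 points at 5-10% early drop-out unrelated to outcome. Drop-out rate, response rate and visit correlations are all assumptions, so this is a range and not an estimate for this trial. The FPG sensitivity analyses share the mechanism, with no size attached.

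A reader might infer more than the documents support:
- **That the primary result is biased.** SAP 4.4.1 uses a not-at-random method with no weights in the imputation or the ANCOVA.
- **That the main tests 1, 2, 4 and 5 are biased in this way.** They rest on not-at-random methods. Wash-out (4.1.12.3) leaves weight out of the imputation model. The retrieved drop-out method (4.1.12.2) may be run by weight, but its donors are themselves subjects who discontinued, so they are only partly selected for response.
- **That the MCMC step in 4.1.12.1 fills Week 26 from responders.** It fills only what is needed for a monotone pattern. Week 26 is the last short-term visit, so its missing values are filled later, here under 4.1.12.5.
- **That responders are the only donors.** Weight 1 also covers anyone on treatment who was not re-randomised for another reason.

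**What to change.** In SAP 4.1.12.1 and 4.1.12.5, for the weighted MAR sensitivity analyses (4.5.2.1, 4.5.3.1, 4.5.5.1, 4.5.6.1):
- Impute subjects who stopped before the second randomisation from a model fitted to all completers of that regimen, meaning responders plus that regimen's re-randomised non-responders, using the W1 or W2 weights. The weights matter. With 38% responders, an unweighted pool would be 0.38/(0.38 + 0.62/2) = 55% responders.
- Keep by-weight imputation only for subjects who reached the second randomisation.
- Keep weight 1 for early drop-outs in the ANCOVA.
- Reconcile the donor descriptions in 4.1.12.5 and 4.4.2.1, and state for each analysis whether weight enters the imputation.

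The cost is SAP wording and a second, weighted donor pool per regimen in the imputation program. No data collection, sample size or confirmatory test changes.

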4.1.12.2 Retrieved Drop-Outs Multiple Imputation Method

Missing HbA1c/FPG data will be imputed separately by treatment regimen of each drug (i.e., low-dose, low-dose/high-dose, and placebo) and weight (as applicable). Subjects not going through up-titration randomisation due to discontinuation of study medication will be assigned a weight of 1 and imputed in the both the low-dose and low-dose/high-dose regimens.

Using monotone datasets generated as described in Section 4.1.12.1, the remaining missing HbA1c/FPG data will be imputed separately for each treatment group and weight (as applicable) using a REGRESSION method in conjunction with the MONOTONE statement and the MNAR statement of the SAS MI procedure.

- Step 1: The imputation model used to create monotone data pattern (see Section 4.1.12.1) will include factors and covariates in the following order: indicators representing randomisation strata of sex, age group and background medication, baseline HbA1c/FPG as well as HbA1c/FPG from all visits per protocol up to Week t.
- Step 2: Using an imputation model with terms for indicators representing randomisation strata of sex, age group and background medication, baseline HbA1c/FPG followed by Week t HbA1c/FPG, for each treatment regimen and weight, subjects that discontinue treatment prior to Week t with baseline and an (off-treatment) Week t assessment available will be used to impute within each missing Week t values (for that treatment regimen) after baseline. Separate models will be performed for each treatment regimen and weight (as applicable) to impute Week t missing data in the multiply imputed monotone datasets generated by Step 1. For this step, one imputation will be performed for each of the 200 imputed datasets from Step 1 to form “complete datasets”.
- Step 3: Imputed values from each of the 200 imputation datasets selected from Step 2 and the non-missing data will be used to calculate change from baseline. The HbA1c/FPG change from baseline values at Week t will be analysed by an ANCOVA with terms for baseline HbA1c/FPG, randomisation strata, and treatment group as described in Section 4.1.9. In case of non-convergence, the imputation and ANCOVA model will be simplified by removing/collapsing the randomisation strata indicator variables in a stepwise manner as described in Section 4.1.

- Step 4: Results from each ANCOVA model will be combined as described in Section 4.1.12.4.

If convergence in all treatment regimens (including placebo) is still not achieved the alternative imputation method (MI-washout) will be used.

4.1.12.3 Wash-out multiple imputation method

Using the monotone datasets generated as described in Section 4.1.12.1, the remaining missing data will be imputed separately for each treatment group using a REGRESSION method in conjunction with the MONOTONE statement and either MNAR statement (for dapagliflozin/saxagliptin treatment groups) or MAR (for placebo treatment group) of the SAS MI procedure. Weight will not be included in the imputation model.

- Step 1: The imputation model used to create monotone data pattern (see Section 4.1.12.1) will include factors and covariate in the following order: indicators representing randomisation strata of sex, age group and background medication, baseline HbA1c/FPG as well as HbA1c/FPG from all visits per protocol up to Week t.
- Step 2: For subjects from dapagliflozin/saxagliptin treatment group, Week t data from the placebo group subjects with non-missing baseline will be used in modelling the MNAR process. The imputation model will include, in the following order, indicators representing randomisation strata of sex, age group and background medication as well as, baseline HbA1c/FPG and Week t HbA1c/FPG.

While for subjects from placebo treatment group, missing data will be imputed sequentially at each assessment using a MAR imputation based on all non-missing data from that visit and data from all prior visits (after imputation). The indicators representing randomisation strata will be included in modelling the MAR processes in the same order as described in Step 1. Therefore, the model will include, in the following order, indicators representing randomisation strata of sex, age group and background medication as well as, baseline HbA1c/FPG, and HbA1c/FPG from all visits per protocol prior to and including Week t.

- Step 3: Imputed values from each of the 200 imputation datasets selected from Step 2 and the non-missing data will be analysed by ANCOVA applied at Week t, with terms for baseline HbA1c/FPG, randomisation strata and treatment group as described in Section 4.1.9. In case of non-convergence, the imputation and ANCOVA model will be simplified by removing/collapsing the randomisation strata indicator variables in a stepwise manner as described in Section 4.1.
- Step 4: Results from each ANCOVA model will be combined as described in Section 4.1.12.4.

4.1.12.4 Combining multiple imputation results

Continuous endpoints

The analysis model will be evaluated in each of the imputed datasets, and the point estimates and SEs will be combined using Rubin's rules to produce valid global estimates with corresponding CIs and p-values. SAS MIANALYZE procedure will be used for this purpose.

Categorical endpoints

HbA1c will be categorised as $< 7\%$ (responders) or $\geq 7\%$ (non-responders) and will be derived from dichotomising the imputed continuous values of HbA1c.

A logistic regression (the SAS LOGISTIC procedure) will be used when there are at least 5 responders by treatment regimen. If there are less than 5 subjects in any treatment regimen, the Fisher's exact test will be used.

- If the logistic model is used, prior to applying Rubin's rules (as described in Section 4.1.12.4) the odds ratio and its SE will be log-transformed (as detailed below).

If Fisher's exact test is used, the final estimates for the proportion of responders, difference in proportion of responders and p-value will correspond to the median of these estimates across all imputed data sets.

Log-transformation of odds ratio estimates

Rubin's combination rules assume that the multiple imputation estimates are asymptotically normally distributed. However, the estimates of odds ratios follow a log-normal distribution. A log transformation can be used to normalise these estimates in order to be able to apply Rubin's combination rules, as follows:

- Obtain log-transformed odds ratio (OR) and SE from each imputed dataset
 $\log_OR = \log(OR)$
 $\log_OR_SE = \log(upper_CI) - \log(lower_CI) / (2 * 1.96)$
- Combine transformed estimates using MIANALYZE
- Back-transform combined estimates (ESTIMATE and STDERR are the results from PROC MIANALYZE):
 $Pooled_OR = \exp(ESTIMATE)$
 $Pooled_lower_CI = pooled_OR * \exp(-1.96 * STDERR)$
 $Pooled_upper_CI = pooled_OR * \exp(+1.96 * STDERR)$

The above code assumes that 95% CIs are used. If different width is required, the 1.96 multiple will need to be adjusted accordingly.

Further information and the SAS code can be found in Reference 4.

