4.1.10 Proportion of subjects with a pre-defined characteristic (responders) at Week t

The proportion of subjects with a *pre-defined characteristic (responders)* at Week t will be analysed using a weighted or unweighted logistic regression when there are at least 5 responders by treatment group. For proportion of responders (e.g., meeting HbA1c criteria), estimates, confidence intervals, and tests will be obtained using a weighted or unweighted logistic regression. Odds ratios (and corresponding standard errors [SE]) representing the responder odds in the dapagliflozin/saxagliptin treatment group (or regimen) versus placebo group will be generated adjusted for baseline variable (e.g., adjustment for baseline HbA1c) and each randomisation stratification factor using the SAS LOGISTIC procedure.

The frequencies of response/non-response and the associated crude response rates (as percentages) will be presented by treatment group (or regimen). In addition, weighted or non-weighted adjusted percentages, standard errors, and 95% CIs for each treatment group (or regimen) will also be displayed. Adjusted odd ratio and corresponding 95% Log likelihood confidence interval, and p-values (uncorrected) will also be presented.

For the HbA1c responder endpoints, if there is no missing data for all treatment groups in the analysis at Week t, then the logistic regression model or Fisher's exact test will be run on the non-imputed data and no combining of results from each imputed data set is necessary.

In case of non-convergence because of sparse data subsequent backup models will be used in removing randomisation strata in sequential order and/or collapsing the randomisation strata of background medication as defined in Section 4.1. A subsequent back-up model in the order presented Section 4.1 will only be provided if the preceding back-up model does not converge.

When there are less than 5 responders in any treatment group, the unadjusted (and difference) proportions, weighted or non-weighted exact 95% confidence interval, and p-values from the weighted or unweighted Fisher's exact test (when applicable) will be provided.

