For each drug (dapagliflozin or saxagliptin) if the primary endpoint is significant, the statistical tests will be formally evaluated, starting from the first secondary efficacy endpoint and continuing in the order above. Each secondary endpoint for a given drug will be tested if the previous secondary endpoint is significant at the two-sided 0.05 level. The testing procedure will stop at the first secondary endpoint that does not reach statistical significance. From then onwards, p-values and CIs will continue to be reported, but no claim will be based these p-values. A clear distinction will be made between p-values whereby claims can and cannot be made.

Hierarchical testing of the primary and secondary efficacy endpoints will be presented for either the Randomised Subjects Data Set or Up-titration Randomised Subjects Data Set (as applicable per endpoint). Point estimates, 95% CIs and p-values will be summarised.

4.5.2 Comparison of mean reduction in HbA1c from baseline at Week 26 between the low-dose/high-dose treatment regimen and placebo

Data will be multiply imputed based on the same approach as described for the primary analysis of the primary endpoint in Section 4.4.1 at all scheduled time points up to and including Week 26, and will include all data regardless of rescue medication initiation or adherence. Analysis will be performed by fitting the weighted ANCOVA model described in Section 4.1.9. The analysis model will be evaluated in each imputed data set and the results will be combined using Rubin's rules as described in Section 4.1.12.4.

The weight matrix W1 described in Section 4.1.9 for the comparison of the low-dose/high-dose treatment regimen versus placebo will be used for this analysis.

In addition, a line plot of LS mean \pm 95% confidence interval (CI) by visit up to Week 26 will be displayed.

4.5.2.1 Sensitivity analysis for secondary endpoint of change from baseline in HbA1c at Week 26 between the low-dose/high-dose treatment regimen and placebo excluding data following rescue medication initiation/early treatment discontinuation

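### As printed, the SE formula for the log odds ratio divides only the lower limit, so no pooled logistic odds ratio above 1 can reach significance

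*SAP*

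**What the plan says.** SAP 4.1.12.4 describes how responder results are combined over the 200 imputed data sets when logistic regression is used. Before Rubin's rules are applied, "the odds ratio and its SE will be log-transformed (as detailed below"). The detail has three steps.

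1. "Obtain log-transformed odds ratio (OR) and SE from each imputed dataset". The log odds ratio is the log of the estimate. The SE is built from the confidence limits: log of the upper limit, minus log of the lower limit, with the line ending "lower_CI) / (2 * 1.96" and a closing bracket. Nothing encloses the subtraction.
2. "Combine transformed estimates using MIANALYZE".
3. The pooled estimate is exponentiated, and the limits are the pooled odds ratio times exp(±1.96 × pooled SE).

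The section adds that "The above code assumes that 95% CIs are used" and refers to its Reference 4 for the SAS code.

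SAP 4.1.10 defines the odds ratio as "representing the responder odds in the dapagliflozin/saxagliptin treatment group (or regimen) versus placebo group". A responder has HbA1c below 7%, so benefit is an odds ratio above 1. The same section plans to present the "Adjusted odd ratio and corresponding 95% Log likelihood confidence interval".

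In SAP 4.5.1 the responder comparisons are items 6, 7, 8 and 11 of eleven ordered tests. "Each secondary endpoint for a given drug will be tested if the previous secondary endpoint is significant at the two-sided 0.05 level", and testing stops at the first failure.

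**The concern.** Division is carried out before subtraction, so the printed line divides only the log of the lower limit by 3.92. The result grows with the odds ratio itself and is not a standard error. The introductory sentence does not rescue it, because the SE of a log odds ratio is not the log of an SE.

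This quantity goes into Rubin's rules, so it sets the pooled p-value and confidence interval for tests 6, 7, 8 and 11 for each drug whenever they are pooled from logistic models. The related sensitivity and metformin-subgroup analyses are affected too, as is the Week 52 responder analysis, which is exploratory. If test 6 cannot succeed, tests 7 to 11 cannot be claimed. That includes items 9 and 10, the high-dose against low-dose comparisons of HbA1c and FPG, which do not use the formula at all.

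**Working it through.** **Inputs.** The SE line, the multiplier 1.96 (so 2 × 1.96 = 3.92) and the back-transformation are from SAP 4.1.12.4. The two-sided 0.05 level is from SAP 4.5.1. The SAP gives no expected responder rates, so the SEs in the examples are assumptions. The bound in step 2 does not depend on them.

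**Step 1: round trip.** Take a known log odds ratio b with SE s. The 95% limits on the log scale are ln U = b + 1.96s and ln L = b − 1.96s.

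- As printed: ln U − ln L/3.92 = b(1 − 1/3.92) + s(1.96 + 0.5) = 0.7449b + 2.46s.
- With brackets: (ln U − ln L)/3.92 = 3.92s/3.92 = s.

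Only the bracketed form returns the SE that produced the limits.

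**Step 2: bound for an odds ratio above 1.** For any interval that contains its estimate, symmetric or not, ln U ≥ b and ln L ≤ b. The printed SE is therefore at least b − b/3.92 = 0.7449b, and z = b/SE ≤ 1/0.7449 = 1.3425. The corresponding two-sided normal p-value is 0.179.

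**Step 3: the bound survives pooling.** Rubin's total variance is at least the mean of the squared SEs, which is at least the square of the mean SE. When the pooled log odds ratio is positive, that is at least (0.7449 × pooled log odds ratio)². So pooled z is again at most 1.3425. As 1.96 × 0.7449 = 1.46 exceeds 1, the pooled lower limit always lies below 1. A numerical check on 20,000 random sets of 200 imputed results, with asymmetric limits allowed, gave a largest pooled z of 1.342.

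**Step 4: examples (identical result in every imputed data set).**

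| OR | Assumed SE | Correct 95% CI | Correct p | Printed SE | p as printed | 95% CI as printed |
|---|---|---|---|---|---|---|
| 2.0 | 0.35 | 1.01–3.97 | 0.048 | 1.377 | 0.615 | 0.13–29.7 |
| 3.0 | 0.40 | 1.37–6.57 | 0.006 | 1.80 | 0.54 | 0.09–102.6 |
| 10 | 0.35 | 5.04–19.9 | <0.001 | 2.576 | 0.37 | 0.06–1559 |
| 100 | 0.01 | 98.1–102.0 | <0.001 | 3.455 | 0.18 | 0.115–87285 |

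The second row in full: ln 3 = 1.099; printed SE = 0.745 × 1.099 + 2.46 × 0.40 = 1.80; z = 1.099/1.80 = 0.61.

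In terms of response rates, assume 35% against 15% with 70 per arm. The odds ratio is 3.05 with SE 0.418. The correct p-value is 0.008; the printed formula gives 0.55.

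**Step 5: odds ratios below 1.** Here the printed SE is 2.46s − 0.7449|b|. With symmetric limits the 0.05 boundary happens to be preserved: |b|/(2.46s − 0.7449|b|) > 1.96 rearranges to 2.46|b| > 1.96 × 2.46s, that is |b|/s > 1.96. The p-value and interval are still wrong. An odds ratio of 0.4 with SE 0.40 has p = 0.022; as printed the SE is 0.30 and p = 0.002. For stronger effects the SE becomes negative: an odds ratio of 0.30 with SE 0.35 gives −0.036.

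**The case against.** The best defence is that this is a missing bracket and not a wrong method. The section's aim is plain (an SE recovered from a 95% interval), only the bracketed form serves it, and the SAP sends the reader to an outside source for the SAS code. The program may well be right. That source and the program could not be examined, so nothing here shows that the analysis was run with the error. Brackets lost when the PDF was read cannot be fully excluded either, although the other brackets in the same block survived.

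The scope is also limited, and these limits stand:

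- Comparisons with too few responders go to Fisher's exact test, and with no missing data nothing is pooled. Neither route uses the formula.
- Test 6 is formally evaluated only if the primary test and secondary tests 1 to 5 have all succeeded for that drug.
- At Week 52 only an exploratory interval and p-value are at stake.
- SAP 4.1.12.4 does not say which type of interval supplies the limits, so asymmetry of likelihood limits is a possibility and not an established fault.

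None of this makes the printed line correct. No other formula appears in the SAP, and its table of changes from the protocol (Table 12) is silent on it. A programmer and an independent validator who both follow the text would agree on the wrong answer.

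**Conclusion.** The formula is wrong as written. For pooled logistic responder analyses with an odds ratio above 1, z cannot exceed 1.3425 and p cannot fall below about 0.18. This is algebra: it needs no assumed response rate, and it holds for asymmetric limits and after Rubin's rules. It rests on reading the line with ordinary operator precedence and on the odds ratio being expressed so that benefit exceeds 1, as SAP 4.1.10 defines it against placebo. Applied literally, it makes test 6 unwinnable for a benefit and closes the hierarchy from that point for either drug. It is probably a slip of notation, but it stands in the rule that governs confirmatory p-values and must be corrected.

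**What to change.** Preferably, pool the log odds ratio and its standard error as they come from the logistic model's parameter table in each imputed data set. The SE then need not be rebuilt from confidence limits, and any asymmetry of likelihood limits no longer matters.

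At a minimum, bracket the difference: SE = (ln U − ln L)/(2 × 1.96). Reword the introductory sentence so that it refers to the SE of the log odds ratio and not to a log-transformed SE.

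Then confirm that the production and validation programs use the corrected form. A simple test is to feed in identical data sets and check that the pooled interval equals the input interval.

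The cost is one line in the SAP and, if needed, one line of program. No design, data or sample-size change follows.
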